9.3. Safety Evaluations

9.3.1. Endpoints

Safety and tolerability endpoints:

- AEs until Week 96 and local and systemic reactogenicity rates for 8 days after each vaccination.
- Discontinuations from vaccination/from study due to AEs.
- SAEs during the course of the study.

9.3.2. Evaluations

Any clinically relevant safety-related changes that occur during the study must be recorded in the CRF.

Any clinically significant abnormalities persisting at the end of the study/early withdrawal will be followed by the investigator until resolution or until a clinically stable endpoint is reached.

The study will include the following evaluations of safety and tolerability according to the time points provided in the Time and Events Schedule:

Adverse Events

AEs will be recorded from signing of ICF until the final visit of the main study (Week 96). SAEs (including HIV infection and abnormal pregnancy outcome) will be recorded for the duration of the study, including the optional LTE phase (Group 1 and Group 2 only). AEs will be followed by the investigator as specified in Section 12.

Details regarding the PSRT and the DMC are provided in Sections 11.7 and 11.8, respectively.

Cardiac-Related Events

At study visits, subjects will be specifically questioned about cardiac-related events, including chest pain/pressure, shortness of breath, and peripheral edema. Any suspicion of a cardiac event will be evaluated clinically by history and physical examination, ECG (read by a central reading cardiologist), and quantitative troponin assay. In the event of an elevation of troponin and/or pathologic ECG changes, the subject will be sent for evaluation by a local cardiologist.

Solicited Adverse Events

Solicited AEs are precisely defined events that subjects are specifically asked about and which are noted by subjects through the memory aid. The investigator or his/her designee should discuss the information from the memory aids with subjects, document relevant information in the clinic chart (source document) and complete the relevant parts of the CRF as described in the CRF Completion Guidelines.

Injection Site (Local) Reactions

Subjects will be asked to note occurrences of erythema, induration and swelling (measured using the ruler supplied), and pain/tenderness, itching, or warmth at the injection site daily for 8 days post-vaccination (day of vaccination and the subsequent 7 days). These occurrences should be recorded through the memory aid provided to serve as a reminder to the subject for the next clinic visit.

Solicited Systemic AEs

Subjects will be instructed on how to record daily temperature using a thermometer provided for home use. Subjects should record oral temperature in the evening post-vaccination, and then daily for the next 7 days through the memory aid. Temperature should be measured at approximately the same time each day. If more than one measurement is made on any given day, the highest daily temperature will be used in the CRF. Fever will be recorded by the investigator or his/her designee for temperatures equal to or higher than 38.0 °C.

Subjects will also be instructed on how to note daily symptoms through the memory aid for 8 days post-vaccination (including the day of vaccination) of the following events:

- fatigue
- headache
- myalgia
- arthralgia
- chills
- fever
- nausea
- vomiting
- rashes
- general itching

Clinical Laboratory Tests

Blood samples for serum chemistry and hematology will be collected at times specified in the Time and Event Schedule. The investigator must review the laboratory report, document this review, and record any clinically relevant changes occurring during the study in the AE section of the CRF. The laboratory reports must be filed with the source documents.

In case a grade 3 or grade 4 laboratory abnormality, or any laboratory abnormality accompanied by clinically relevant signs or symptoms occurs (from the baseline visit onwards), a confirmatory test should be performed within 48 hours after the results have become available. After that, laboratory tests will be repeated weekly until values are resolved or stable.

The following tests will be performed by a local laboratory (*parameters only measured at screening):

- **Serum chemistry**

| | |
|-------------------------------|-----------------------------------|
| sodium* | alkaline phosphatase* |
| potassium* | phosphate* |
| chloride* | albumin* |
| calcium* | total protein* |
| magnesium* | bilirubin* |
| bicarbonate* | AST |
| blood urea nitrogen (BUN)* | ALT |
| glucose* | creatinine |
| creatine phosphokinase (CPK)* | troponin |
| | FSH (post-menopausal women only)* |

- **Hematology**

hemoglobin

hematocrit
red blood cell (RBC) count
white blood cell (WBC) count with differential
platelet count

- **Urinalysis** – dipstick for
specific gravity
pH
glucose
protein
blood
ketones

Microscopic reflex testing will be carried out in the event of positive urinalysis tests.

Laboratory values will be graded according to a modified version of the DAIDS Table for Grading the Severity of Adult and Pediatric Adverse Events (DAIDS AE Grading Table), Version 1.0 dated December 2004 (Clarification, August 2009) included in [Attachment 1](#), and, if clinically significant, reported as AEs.

Additional clinical laboratory assessments to be performed are as follows:

- Serum pregnancy testing (β -hCG) for women of childbearing potential at screening
- Urine pregnancy testing for women of childbearing potential pre-dose on Day 1, Weeks 12, 24, 48, 60, 96 and at the early exit visit. A urine pregnancy test will also be carried out prior to mucosal secretion collection, for those females who have consented to this procedure.
- Troponin at screening
- Serology: hepatitis B, and hepatitis C at screening
- Syphilis, chlamydia, gonorrhea and trichomonas at screening, and additionally at Weeks 2, 14, 26, 50, 60, and 96 for subjects who consent to mucosal secretion collection
- HIV testing at screening, pre-dose on Day 1, Weeks 12, 24, and 48, and additionally at Weeks 78 and 96, at the early exit visit and at each visit of LTE phase.

Electrocardiogram (ECG)

Supine 12-lead ECGs will be performed at screening and at Week 16, and only performed again during the study if clinically indicated based on signs and symptoms.

For 30 minutes prior to the ECG, subjects should refrain from meals, hot or cold beverages and strenuous exercise, and should remain in a room with a comfortable temperature. Each ECG should be obtained after the subject has been at rest for at least 5 minutes. ECG interpretation/comparison will be provided by a central reading cardiologist.

Computer-generated interpretations of ECGs should be reviewed for data integrity, reasonableness and for immediate safety assessment by the investigator or appropriately delegated healthcare provider. Digital ECG data will be transmitted to a centralized ECG over-read service provider. Over-read of the ECGs will be transmitted back to the site within 72 hours. The centralized ECG over-read data will be considered source data.

Vital Signs

Vital sign measurements will be performed at time points specified in the Time and Events Schedule. Blood pressure and pulse/heart rate measurements should be preceded by at least 5 minutes of rest in a quiet setting without distractions.

The following measurements will be performed:

- Heart rate (beats per minutes, bpm), systolic blood pressure (mmHg) and diastolic blood pressure (mmHg). Confirmatory vital signs measurement can be performed if inconsistent with a prior measurement
- Body temperature (oral)

If any clinically significant changes in vital signs are noted, they will be reported as AEs and followed to resolution, or until reaching a clinically stable endpoint.

Physical Examination

Full physical examination, including height and weight, will be carried out at screening and at the final visit of the main study (Week 96). At all other visits, an abbreviated, symptom-directed exam will be performed as indicated by the investigator based on any clinically relevant issues, clinically relevant symptoms and medical history. Symptom-directed physical examination may be repeated if deemed necessary by the investigator. Weight will be measured at every visit.

Physical examinations will be performed by the investigator or designated medically-trained clinician. Any screening or baseline abnormality should be documented in the medical history page of the CRF. Any clinically relevant post-baseline abnormality or any clinically relevant worsening versus baseline conditions should be documented in the AE pages of the CRF.

9.4. HIV Testing and VISP

9.4.1. HIV Testing

At screening, subjects will be tested for HIV infection, and must be negative to be entered into the study. If possible, the site should select an assay that is US FDA-approved.

After screening, diagnostic HIV testing will be performed during the study as indicated in the Time and Events Schedule. An HIV testing algorithm (detailed in the Study Procedures Manual) will be followed. Information provided to the clinical staff of the study site will not include the results of specific tests, but will state only the final interpretation as “infected” or “uninfected”. This system allows timely HIV testing without compromising the double-blind nature of the

study. The algorithm used for HIV testing throughout the main phase of the study aims to differentiate false-positive results (Vaccine Induced Seropositivity [ViSP]) from true positives (HIV infection).

If a false-positive HIV test develops during the study, further HIV testing will be offered via post-study follow up. (See Section [9.4.3](#) for more details on ViSP).

9.4.2. Management of Subjects who Become HIV-infected During the Study

Test results performed to confirm the diagnosis will be forwarded to the study staff. Subjects who become HIV-infected during the study will (see Section [12.3.3](#)):

- be excluded from further vaccinations
- be provided counseling and referred for medical treatment
- be informed about observational studies monitoring subjects with HIV infection

9.4.3. Vaccine Induced Seropositivity (ViSP)

In general, HIV-uninfected subjects who participate in preventative HIV vaccine studies may develop HIV-specific antibodies as a result of an immune response to the candidate HIV vaccine, referred to as ViSP. These antibodies may be detected in common HIV serologic tests, causing the test to appear positive even in the absence of actual HIV infection. ViSP may become evident during the study, or after the study has been completed.

Should a subject receive a positive result in an HIV antibody test during the study, the site will carry out a follow-up testing algorithm either to exclude or confirm HIV infection. Further details of this algorithm are given in the Site Procedures Manual.

Subjects should not donate blood during the study. Blood donation options for those subjects who wish to resume blood donation will be explained at the final study follow-up visit.

In the case of ViSP, if, either during the study or after the end of the study, a subject requires an HIV test outside the study (eg, to obtain a travel visa or insurance, or for medical reasons), he/she should contact the research center. The center can issue a written statement giving details on ViSP and on the testing algorithm to be followed. If requested by a subject, repeat HIV testing will be available at the site at most every three months, to confirm their HIV-status. More frequent testing is only allowed after sponsor approval. Testing for a particular subject will be available as long as ViSP is present for this subject.

Depending on the local availability of a follow-up protocol, subjects could join into such a study that specifically follows the course of ViSP. Such a study may not be available at all sites. However, if such a study is not available, the site will provide HIV testing on request as described in the previous paragraph.

In addition to providing testing, subjects will always receive pre- and post-test counseling.

9.4.4. Social Impact

Subjects in preventive HIV vaccine clinical studies may experience problems with personal relationships, employment, education, health care, housing, health, disability or life insurance, travel and immigration. In relation to a subject's family, friends and/or colleagues, the social impact could manifest in one or more ways, resulting in social conflicts and stigmatization:

1. The investigational vaccine is thought to be harmful to the subject's health, including a belief that it might cause HIV infection.
2. The subject is perceived as HIV-infected or at high risk.
3. Repercussions from any VISP.

For these reasons, subjects will complete a social impact questionnaire at Weeks 24, 48, 96, and at each visit of the LTE phase as specified in the **TIME AND EVENTS SCHEDULE** to evaluate any potential consequences of the subject's participation.

9.4.5. Post-Exposure Prophylaxis (PEP)

In case a subject believes he/she might have been exposed to HIV, he/she should contact the study site as soon as possible. Treatment will be determined by the investigator or his designee, in accordance with local PEP guidelines. The sponsor should be informed as soon as possible. PEP medication will be reimbursed by the sponsor during study participation. HIV prevention counseling will be provided. In case a subject has recurrent need for PEP, eligibility of the subject (with regards to HIV-risk profile) to continue in the study will be re-assessed.

9.5. Sample Collection and Handling

The actual dates of sample collection must be recorded in the CRF or laboratory requisition form. Refer to the Time and Events Schedule for the timing and frequency of all sample collections.

Instructions for the collection, handling, storage, and shipment of samples for immunogenicity assay are found in the Laboratory Manual that will be provided. Collection, handling, storage, and shipment of samples must be under the specified, and where applicable, controlled temperature conditions as indicated in the Laboratory Manual.

10. SUBJECT COMPLETION/WITHDRAWAL

10.1. Completion

A subject who is not participating in the long-term extension period will be considered to have completed the study if he or she has completed the assessments at Week 96. A subject who is participating in the long-term extension period will be considered to have completed the main study if he or she has completed the assessments at Week 96 and will be considered to have completed the LTE phase if he or she has completed the assessments at the last visit of the extension period (Week 336).

10.2. Discontinuation of Study Vaccine

Subjects will be withdrawn from study vaccine administration for the reasons listed below. These subjects must not receive any additional dose of study vaccine but should enter the follow-up phase, starting from Visit 14 onwards. Additional unscheduled visits may be performed for safety/tolerability reasons, if needed. These subjects are not eligible for the LTE phase.

- Anaphylactic reaction following vaccination
- Pregnancy
- Any related* SAE
- Any related* AE, worsening of health status or intercurrent illnesses that, in the opinion of the investigator, requires discontinuation from study vaccine
- Confirmed HIV infection
- Chronic or recurrent use of immunosuppressants (see Section 8)
- Missing more than 1 study vaccination (see Section 6).

*AEs deemed by the investigator to be very likely, probably, or possibly related to study vaccine.

10.3. Contraindications to Vaccination

The following events constitute a contraindication to vaccination at that point in time. If any of these events occur at the scheduled time for vaccination, the vaccination can be rescheduled (as long as this is in agreement with the allowed windows, see Section 9.1.2):

- Acute illness at the time of vaccination. This does not include minor illnesses such as diarrhea or mild upper respiratory tract infection.
- Fever (oral temperature $\geq 38.0^{\circ}\text{C}$) at the time of vaccination.

10.4. Withdrawal from the Study

Each subject has the right to withdraw from the study at any time for any reason without affecting the right to treatment by the investigator. The investigator should make an attempt to contact subjects who did not return for scheduled visits or follow up. Although the subject is not obliged to give reason(s) for withdrawing prematurely, the investigator should make a reasonable effort to ascertain the reason(s) while fully respecting the subject's rights.

A subject will be withdrawn from the study for any of the following reasons:

- Repeated failure to comply with protocol requirements
- Decision by the sponsor or the investigator to stop or cancel the study
- Decision by local regulatory authorities and Institutional Review Board/Independent Ethics Committee (IRB/IEC) to stop or cancel the study
- Lost to follow up

- Withdrawal of consent
- Death

If a subject is lost to follow up, every reasonable effort must be made by the study site personnel to contact the subject and determine the reason for discontinuation/withdrawal. The measures taken for at least three efforts to follow up must be documented.

When a subject withdraws before completing the study, the reason for withdrawal is to be documented in the CRF and in the source document. Study vaccine assigned to the withdrawn subject may not be assigned to another subject. Enrollment will be stopped when 400 subjects have received at least one vaccination. If a subject withdraws early from the study, assessments for early withdrawal should be obtained (see Section [9.1.7](#)).

Subjects who wish to withdraw consent from participation in the study will be offered a single exit visit for safety follow-up (prior to formal withdrawal of consent). They have the right to refuse. The exit visit is only applicable to the main study until Week 96.

A subject who withdraws from the study will have the following options regarding optional research samples:

- The collected samples will be retained and used in accordance with the subject's original informed consent appendix for optional research samples.
- The subject may withdraw consent for optional research samples, in which case the samples will be destroyed and no further testing will take place. To initiate the sample destruction process, the investigator must notify the sponsor study site contact of withdrawal of consent for the optional research samples and to request sample destruction. If requested, the investigator will receive written confirmation from the sponsor that the samples have been destroyed.

Withdrawal From the Optional Research Samples While Remaining in the Main Study

The subject may withdraw consent for optional research samples while remaining in the study. In such a case, the optional research samples will be destroyed. The sample destruction process will proceed as described above.

Withdrawal From the Use of Samples in Future Research

The subject may withdraw consent for use of samples for future research (refer to Section [16.2.5](#)). In such a case, samples will be destroyed after they are no longer needed for the clinical study. Details of the sample retention for research are presented in the main ICF.

11. STATISTICAL METHODS

Statistical analysis will be done by the sponsor or under the authority of the sponsor. A general description of the statistical methods to be used to analyze the immunogenicity and safety data is outlined below. Specific details will be provided in the Statistical Analysis Plan.

The primary analysis will be performed once all subjects have completed the Week 28 visit (ie, 4 weeks after the third injection) or discontinued earlier. The purpose of this analysis is to allow for an early conclusion on regimen selection for future studies, based on immunogenicity and safety. An additional analysis will be performed once all subjects have completed the Week 52 visit (ie, 4 weeks after the fourth injection) or discontinued earlier. The final analysis of the main study will be performed once all subjects have completed their final study visit at Week 96 (ie, including the second year follow-up period) or discontinued earlier. The final analysis of the LTE phase (optional and only for a subset of subjects) will be performed once all included subjects have completed the last visit of the extension period (Week 336), or discontinued earlier.

11.1. Analysis Populations

The safety population will consist of all subjects who received at least one dose of study vaccine, and for whom any post-dose data is available.

The immunogenicity population will consist of all subjects who received at least one dose of study vaccine, and who have data from at least one post-dose blood sample.

The per-protocol population will consist of all subjects who have received at least the first three vaccinations according to the protocol-specified vaccination schedule, have at least one measured post-dose blood sample collected, and who have no major protocol violations impacting immunogenicity assessments.

11.2. Sample Size Determination

A sample size of 50 subjects per regimen is regarded to be appropriate to assess the safety and tolerability of the different vaccine regimens and also collect sufficient data on immunogenicity. Placebo recipients are included for blinding and safety purposes and will provide control specimens for immunogenicity assays.

While mild to moderate vaccine reactions (local injection site and systemic responses) are expected, AEs that preclude further dose administration or more serious ones that would limit product development are not anticipated. With 50 individuals in a vaccine regimen, the observation of 0 such reactions would be associated with a 95% confidence that the true rate is less than 6%. For the combined groups with Ad26.Mos.HIV (n = 350), there would be 95% confidence that the true rate is <1% when 0 events are observed. The following table shows the probabilities of observing at least one AE at given true AE rates:

| True AE rate | Probability of observing at least one AE in n subjects | |
|--------------|--|---------|
| | n = 50 | n = 350 |
| 0.1% | 5% | 30% |
| 0.5% | 22% | 83% |
| 1% | 39% | 97% |
| 2.5% | 72% | 100% |
| 5% | 92% | 100% |
| 10% | 99% | 100% |

The primary population for the safety analyses will consist of all subjects who received at least one dose (Ad26.Mos.HIV or placebo).

The immunogenicity population will consist of all subjects who received at least one dose and have at least one measured post-dose blood sample collected. Anticipating a dropout rate of approximately 10%, 45 evaluable subjects per group will allow detection of 2.3-fold differences in Env-binding antibody titers, generally accepted to be biologically relevant, between groups with 80% probability, assuming a two-sided 5% Type I error and a standard deviation of 0.6 on the \log_{10} scale.

Groups will be combined to make comparisons between different viral vectors (groups combined over the different protein doses, N=135 per group) or between different protein doses (groups combined over different viral vectors, N=90 per group). Under the same assumptions as above, this will allow detection of 1.6-fold (N=135/group) to 1.8-fold differences (N=90/group) in Env-binding antibody titers. Potential statistical interactions will be explored by means of the appropriate interaction tests.

Breadth of Env-binding antibody response will be summarized as the number of HIV clades (ranging 0-3, for Clades A, B, C) to which a subject shows an antibody response. Differences in breadth between different regimens will be compared via the Wilcoxon-Mann-Whitney test. Assuming 45 evaluable subjects per group, a two-sided 5% Type I error rate, no correlation between the different clades, and a 90% response rate for every clade (A/B/C) in one group, [Table 7](#) below shows the power to detect a significant difference with various alternative breadths and (combined) group sizes.

Table 7: Power (%) for two-sided 5% test for difference in breadth of response, if the response towards Clade A/B/C in one group is 90%/90%/90%

| N per group | 45 | 90 | 135 |
|------------------------------------|------|-------|-------|
| Lower response for 3 clades | | | |
| 80/80/80 | 61.9 | 88.9 | 97.3 |
| 75/75/75 | 89.0 | 99.4 | >99.9 |
| 70/70/70 | 98.0 | >99.9 | >99.9 |
| Lower response for 2 clades | | | |
| 90/80/80 | 36.0 | 61.6 | 78.7 |
| 90/75/75 | 63.4 | 90.0 | 97.7 |
| 90/70/70 | 84.1 | 98.6 | >99.9 |
| Lower response for 1 clade | | | |
| 90/90/80 | 13.7 | 22.7 | 31.5 |
| 90/90/75 | 24.4 | 42.9 | 58.7 |
| 90/90/70 | 38.3 | 64.9 | 81.7 |

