11.4. Immunogenicity Analyses

No formal hypothesis on immunogenicity will be tested. The analysis of immunogenicity will be done on the immunogenicity and per-protocol populations as defined in Section 11.1.

Descriptive statistics (actual values and changes from reference) will be calculated for continuous immunologic parameters at all time points. Graphical representations of changes in immunologic parameters will be made as applicable. Differences between groups at a specific time point will be tested for exploratory purposes by a 2-sample t-test if the data appear to be normally distributed. If not, the non-parametric Wilcoxon rank sum test will be used. If portions of the measurements are censored below the assay quantification limit, the Gehan-Wilcoxon test will be employed. All statistical tests will be two-sided and will be considered statistically significant if $p<0.05$.

Frequency tabulations will be calculated for discrete (qualitative) immunologic parameters at all time points. Significant differences between groups will be determined by a 2-sided Fisher's exact test.

Magnitude and breadth of (neutralizing) antibody responses will be explored graphically through the generation of individual magnitude-breadth (M-B) curves. The area under the M-B curve (AUC) provides an overall summary of the M-B profile. The AUCs will be compared between groups using the Wilcoxon-Mann-Whitney test.

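### The 1.6-fold and 1.8-fold detectability stated for the pooled vector and protein-dose comparisons assumes that the pooled-over factor has little or no effect, and no analysis is specified that would remove that condition

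*Protocol*

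**What the plan says.** Groups 1 to 6 form a two-by-three layout: an Ad26 or MVA boost, each with 250 mcg, 50 mcg or no gp140. Protocol section 11.2 first sizes the single-arm comparison: "45 evaluable subjects per group will allow detection of 2.3-fold differences in Env-binding antibody titers, generally accepted to be biologically relevant". Power is set at 80%, alpha at 5% two-sided, and the SD at 0.6 in log10 units. It then combines arms. Vectors are compared with "groups combined over the different protein doses, N=135 per group", and protein doses with the two vectors merged, 90 per side. For these it states: "Under the same assumptions as above, this will allow detection of 1.6-fold (N=135/group) to 1.8-fold differences (N=90/group". The next sentence promises that interactions will be explored with suitable tests but names no model.

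On analysis, protocol section 11.4 says: "Differences between groups at a specific time point will be tested for exploratory purposes by a 2-sample t-test". That applies when normality looks plausible. Otherwise it gives a Wilcoxon rank sum test, or a Gehan-Wilcoxon test when some values fall below quantification. None of these is stratified. Section 11 leaves detail to the SAP. SAP section 6.3 has summaries, confidence intervals and plots by group, but no combined comparison and no two-factor model.

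**The concern.** When three arms at different protein levels are merged, the SD of the merged group contains the spread between the arm means as well as the 0.6 within each arm. An unstratified test puts that extra spread into its standard error. The SD of 0.6 can be carried over unchanged only if the factor being pooled over does nothing, whereas estimating the effects of vector and protein dose is the reason for pooling.

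The pooled contrasts are the best-powered comparisons in section 11.2. They address two questions that matter for choosing a regimen: which vector, and how much protein. If gp140 works well, the vector comparison becomes less sensitive than stated, and the reverse holds for the dose comparison. This can be avoided, because both factors are randomised and known for every subject.

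**Working it through.** **Inputs from protocol section 11.2.** Two-sided alpha 0.05, power 80%, SD 0.6 on log10, and 45, 90 or 135 evaluable per side (50 per arm less about 10% dropout). **Assumed, because the documents do not give it:** the effect of the pooled-over factor, taken as 2.3-, 5- and 10-fold.

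**1. Reproduce the stated figures.** Detectable log10 ratio = 0.6 × √(2/n) × (1.960 + 0.842).
- n = 45: 0.354, or 2.26-fold (2.28 with the t distribution); stated 2.3.
- n = 90: 0.251, or 1.78-fold (1.79); stated 1.8.
- n = 135: 0.205, or 1.60-fold (1.60); stated 1.6.

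Power is 79.8% at 1.6-fold and 81.4% at 1.8-fold. So the pooled figures use SD 0.6 with no allowance for spread between arms.

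**2. SD of a pooled group.** Let e be log10 of the assumed effect.
- Vector contrast, pooled over protein, with the two doses equal and the no-protein arm lower by e: S = √(0.36 + 2e²/9).
- Dose contrast, pooled over two vectors: S = √(0.36 + e²/4).

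Example: a 5-fold protein effect has e = 0.699, so S = √(0.36 + 0.1086) = 0.685 and k = S/0.6 = 1.141.

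**3. Detectable ratio, two versions.**
- (b) Fixed arm composition: the true sampling error stays at 0.6 and only the standard error used by the test is inflated. Log10 ratio = 0.6 × √(2/n) × (1.960k + 0.842); power = Φ[log10(ratio)/(0.6√(2/n)) − 1.960k].
- (a) Full inflation: S replaces 0.6 throughout.

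Example, n = 135 and 5-fold: (b) gives 0.0730 × (2.236 + 0.842) = 0.225, or 1.68-fold; (a) gives 0.685 × 0.1217 × 2.802 = 0.233, or 1.71-fold.

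| Assumed effect of other factor | Vector, n = 135: S | ratio (b)–(a) | power at 1.6 | Dose, n = 90: S | ratio (b)–(a) | power at 1.8 |
|---|---|---|---|---|---|---|
| none | 0.600 | 1.60 | 80% | 0.600 | 1.78 | 81% |
| 2.3-fold | 0.624 | 1.62–1.63 | 77–78% | 0.627 | 1.81–1.83 | 78–79% |
| 5-fold | 0.685 | 1.68–1.71 | 69–71% | 0.694 | 1.90–1.95 | 69–72% |
| 10-fold | 0.763 | 1.75–1.82 | 59–62% | 0.781 | 2.01–2.12 | 59–62% |

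**4. Where it starts to matter.** The vector figure reaches 1.65 at a protein effect of about 2.9-fold under (a) or 3.6-fold under (b). The dose figure reaches 1.85 at a vector effect of about 2.8-fold or 3.5-fold. The pattern across doses also counts: a 2.3-fold rise at each of two protein steps gives 1.66 to 1.69 for the vector contrast.

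**5. Direction of the error.** Under (b) the real two-sided type I error is 2 × [1 − Φ(1.960k)]. It is about 2.5% at 5-fold, and 1.3% (vector) or 1.1% (dose) at 10-fold. It is below 5%, never above.

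**6. Check by simulation (20,000 runs; Wilcoxon 4,000).** At a 5-fold effect the t-test had 71% power for both contrasts and the Wilcoxon test 68%. A test stratified by arm stayed between 79% and 81% at every effect size tried.

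**The case against.** The strongest reply is that everything turns on an effect size the documents do not supply. At 2.3-fold, the only difference the protocol calls biologically relevant, the pooled figures still round to 1.6 and 1.8 and power falls by about 2 to 3 points. That stands. So does the point that arm sizes are planned and equal, which makes version (b) the better description of the t-test and (a) an upper bound.

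It can also be said that section 11.4 speaks of differences between groups without mentioning pooled groups, that section 11 is only a general description, and that an interaction test needs both factors in one analysis. This is fair as far as it goes: a wrong test is not expressly prescribed for the combined comparisons. But a promise to explore interactions does not say that the main contrasts will use within-cell error, and the SAP does not fill the gap.

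The protocol's remark that envelope protein dose and antibody response are not clearly correlated (section 1.1) does not settle the matter either. It concerns dose level, not protein against no protein.

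A reader might also infer serious confounding from unequal losses between arms. The documents give no arm-specific losses. As an illustration, losing 5 extra subjects from one no-protein arm under a 5-fold protein effect shifts the vector ratio by 0.699 × (45/135 − 40/130) = 0.018 on log10, or about 1.04-fold. That is a minor side issue.

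Finally, the tests are exploratory, no formal hypothesis is tested, and regimen selection rests on several immunogenicity assessments. This lowers the priority.

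**Conclusion.** The concern holds in conditional form. With the unstratified tests that the protocol names, 1.6-fold and 1.8-fold are correct only if the pooled-over factor has little or no effect, and section 11.2 does not say so. The loss is negligible at 2.3-fold. It is material from about 3-fold, and reaches roughly 10 points of power at 5-fold and 20 at 10-fold. These sizes rest on assumed effects, equal arms of 45 and a common within-arm SD of 0.6.

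A reader might infer that the pooled comparisons simply fail to deliver the stated figures. The documents do not support that, since they give no vector or protein effect, and with none the figures are exact. Nor do they support a worry about false positives, because the unadjusted test is conservative. The sample size needs no change. What is missing is a specified analysis for these comparisons, or a stated condition on the figures.

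**What to change.** - **Protocol section 11.4:** specify that the combined comparisons in Groups 1 to 6 use a linear model on log10 titre with vector and protein dose, adding vector-by-dose for the interaction test already promised in section 11.2. Report main-effect ratios with 95% confidence intervals from within-cell error. Under this analysis the stated 1.6 and 1.8 hold whatever the size of the other main effect.
- **Values below LLOQ or clearly non-normal data:** use a rank test stratified by the other factor, or a censored-data version of the model. Section 11.4 already provides for both situations in its two-group tests, so the replacement must as well.
- **SAP section 6.3:** add the comparison. There is no pooled test there to replace. SAP section 1 says the Week 96 analysis is done and will not be rerun, and the extension covers Groups 1 and 2 only, so no vector contrast can come from it. The model should therefore enter as a labelled supplementary analysis of the Week 28 and Week 52 data.
- **Minimum:** one sentence in section 11.2 saying that 1.6-fold and 1.8-fold assume no effect of the factor pooled over.

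The cost is wording in two documents, one additional model and its output. No new data or samples are needed. Because the data are already unblinded, the supplementary analysis should be described as specified after the results were available.
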